### **Risk/Benefit Assessment - cont.**

- IV) The device is NOT for a use of substantial importance in diagnosing, curing, mitigating, or treating disease, or otherwise preventing impairment of human health that presents a potential for serious risk to the health, safety, or welfare of a subject.
- V) The invisa-RED Technology IR REHAB is to be used only as directed as an adjunctive therapy for nociceptive musculoskeletal pain.
- VI) The device does NOT otherwise present a potential for serious risk to the health, safety, or welfare of a subject.
- VII) The invisa-RED IR REHAB is classified as an FDA Class II device and has passed all FDA electromagnetic compatibility (EMC) standards.
- VIII) The invisa-RED IR REHAB device employs Class 3b laser diodes in a system of "paddles" each containing multiple diodes. Class 3B lasers are hazardous for eye exposure; therefore during therapy protective eyewear is prescribed for staff, the individual undergoing treatment, and any others in the room. Eye safety is further enhanced by standardized invisa-RED Technology IR REHAB clinical procedures, which are designed to eliminate exposure of the eyes of the patient and any proximate individuals to direct laser light. IR REHAB clinical procedures which are found in the manual and are stressed as mandatory during user training dictate that the paddles are to be 1) placed on the area to be treated, 2) secured if required, and then and only then 3) the system is activated and treatment begun. This greatly reduces the chance of any direct laser light entering the eye. Class 3B lasers can heat skin and materials but are not considered a burn hazard. Treatment protocol standards do dictate power settings be adjusted for the patient's Fitzpatrick Scale skin type; as differing skin tones result in a variance in their coefficient of absorption of photonic energy. If these recommendations are not followed the therapy may result in skin sensitivity. Additionally each patient is asked to verbally attest to his or her comfort level at the start of each therapy session and further instructed to notify staff of any skin discomfort at any time during the treatment.

### **Staff and Investigator Training and Certification**

All staff involved in conducting the clinical trial will undergo training and be certified on the use, safety, and clinical procedures of the invisa-RED Technology IR REHAB device. The Primary Investigator and clinical associates conducting the trial will also successfully complete the Collaborative Institutional Training Initiative (CITI) course GCP for Clinical Trials with Investigational Drugs and Medical Devices (U.S. FDA Focus).

**FDA Study NCT06393088**

## **Study Research Questions**

### **Research Question:**

Is there a statistically significant difference in nociceptive musculoskeletal pain after therapy with the IR REHAB device as compared to a sham (placebo) device when used in an approved and standardized clinical protocol?

### **Null Hypothesis:**

There is not a statistically significant difference in nociceptive musculoskeletal pain when using an IR REHAB device when compared with a sham (placebo) device as a therapy in an approved and standardized clinical protocol.

### **Alternative Hypothesis:**

There is a statistically significant difference in nociceptive musculoskeletal pain when using an IR REHAB device when compared with a sham (placebo) device as a therapy in an approved and standardized clinical protocol.

## **Data Sets/Populations**

### **Criteria for Participants:**

Participants will be taken from a random population of respondents to email and social media recruitment, in person offers to participate to existing patients, and individuals in the community who have seen signage advertising the trial. The number of participants is projected to be thirty (30). There will be an equitable distribution of male and female participants. Women who are pregnant, trying to get pregnant, or nursing will be excluded from the study, as they should not receive Low-level Laser Therapy (LLLT). Note; there is no evidence of harm to an unborn baby however there have been no safety tests either, so for medical legal reasons we recommend never treating such individuals. The participants will be older than the age of 18 years. Inclusion criteria will be individuals that may benefit from an adjunctive therapy for nociceptive musculoskeletal pain.

**Exclusion criteria will include the following:**

- For women who are pregnant, trying to get pregnant or nursing, laser light therapy should be received only after the end of these conditions. There is no evidence of harm to an unborn baby however there have been no safety tests either, so for medical legal reasons we recommend against treatment during these times.
- Individuals with hypertension, light sensitive epilepsy, cancer, heart disease, infectious skin disease, and severe varicose veins should not use this device.
- People suffering from infectious and acute disease such as a fever should not use this device.
- People who have hemorrhagic disease, vascular ruptures, skin inflammation, or any disease of the skin should not use this device.
- Person with a history of lentigines, an autoimmune vascular disease that causes color changes in the legs or arms due to obstruction or stenosis of blood vessels.
- A person with a history of erythema, an acquired, long-lasting reticulocyte red and pigmented rash, caused by persistent or repeated exposure to intense heat or infrared radiation.
- Persons who are susceptible to or have a history of herpes in the treatment area
- Anyone who has experienced problems subsequent to previous laser treatments
- People who have immune system dysfunction such as Leukemia, Hemophilia, etc., and light sensitive persons should not use this device.
- Use of laser light therapy in the ears, nose, eye, or throat is not recommended.
- Individuals with a history of melanoma, raised moles, suspicious lesions, keloid scar formation, or healing problems should not undergo laser light therapy
- Individuals with active infections, open lesions, hives, herpetic lesions, cold sores, or tattoos and permanent make-up in the area of treatment should not undergo laser light therapy.
- People who have used isotretinoin (commonly known as Accutane), tetracycline, St. John's Wort, or any photo sensitizing drugs in the last year should not undergo laser light therapy.
- Individuals with autoimmune diseases such as Lupus, Scleroderma, or Vitiligo should not undergo laser light therapy.

## **Exclusion Criteria - continued**

- Individuals who have pacemakers or other electro-stimulation devices surgically implanted should not undergo laser light therapy.
- Any insulin dependent individual should consult their physician before undergoing laser light therapy.
- All individuals considered “vulnerable” such as children, pregnant women, nursing home residents or other institutionalized persons, students, employees, fetuses, prisoners, and persons with decisional incapacity.

## **Analysis**

To examine the research question, independent sample *t*-tests using the statistical analysis program IBM SPSS ver.30 will be conducted on the data set. The data set will be comprised of comparative results from the two trial groups, the Care as Usual Study Group and the Sham (placebo effect) Study Group. The tests will be bootstrapped to a test size of N=20,000 for validation.

An independent samples *t*-test is the appropriate statistical test when the purpose of research is to assess if differences exist on a continuous (interval/ratio) dependent variable by a dichotomous (2 groups) independent variable. The continuous dependent variable to be tested is the change in pain level of the joint or body area treated during the clinical trial. Each participant will be asked to indicate on a standard 100mm Visual Analog Scale their pain levels before the first treatment and after each of the prescribed treatments. The difference between the initial pain level of a participant and the level of pain indicated after their sixth and final treatment will be statistically analyzed to determine if there is a significant difference between those in the Care As Usual Group and the Sham (placebo) Group.

The dichotomous independent variables for the data set is the change in pain level of each participant in the group treated with the invisa-RED Technology IR REHAB Low-level Laser Therapy (LLLT) device and the group treated using the sham (placebo) device as a therapy in the standardized clinical protocol. The assumptions of normality and homogeneity of variance will be assessed. Homogeneity of variance assumes that both groups have equal error variances and will be assessed using Levene's Test for the Equality of Error Variances. Each *t*-test will be two tailed with the probability of rejecting the null hypothesis when it is true set at  $p < 0.05$ . This ensures a 95% certainty that the differences did not occur by chance. Data produced by both groups will be the results of a clinical trial governed and conducted as a randomized single - blind study using an IRB approved clinical protocol.

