## **Methods and Procedures**

The trial is designed to prove the efficacy and safety of the invisa-RED Technology IR REHAB device when used as prescribed as an adjunctive therapy for musculoskeletal pain. The trial will compare results between two groups; the first will be treated using the invisa-RED Technology IR REHAB and the second group with a sham (placebo) device.

The trial will be conducted employing a single blind study methodology; participants will not know to which trial group they have been randomly assigned. Participants randomly selected for the control or Sham (placebo) Group will undergo therapy sessions with a disabled IR REHAB device producing no laser energy, however, this sham device will power up the console and fans to appear to be operating normally. If a participant questions the efficacy of the sham device, an assertion may be made that only a near infrared, non-visible frequency of light, is being employed. The control group receiving treatments using the sham device will be scheduled for treatment at times other than participants who will undergo therapy sessions with the fully functioning device in order to ensure the trial blind.

All participants will undergo treatments 2 times weekly for 3 weeks. Treatment will be 15 minutes each session. For each 15 minute session a singular adjustment to the laser’s power output will be made based on the participants standard Fitzpatrick Skin Type. This power adjustment ensures optimal photonic energy absorption, enhanced efficacy, and participant safety. The minimum time between any participants’ scheduled treatments will be 48 hours.

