## **Methods and Procedures - continued**

Prior to each therapy session the participant will be asked to record their pain level using a Visual Analog Scale (VAS) and then in the same manner after each treatment using the same Visual Analog Scale (VAS). The results from the two groups will be statistically analyzed to determine the efficacy of the invisa-RED Technology IR REHAB as an adjunctive therapy for nociceptive musculoskeletal pain. Any medical errors will be included in the statistical analysis.

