## **Data Analysis and Data Monitoring**

The mean change in each group of participant's pain levels as recorded at the trials beginning and then at the trials conclusion will be statistically evaluated using a two-tailed independent sample T-test with an a priori threshold p value of < (less than) 0.05.

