## Outcome Measures:

1. Primary Outcome	
Title:	Measured Change in the Participants Pain Levels
► Description:	Participants pain levels will be measured using a visual analog scale ...
	If reporting a score on a scale, please include the unabbreviated scale title, the minimum and maximum values, and whether higher scores mean a better or worse outcome.
Time Frame:	Participants will indicate their pain level before and after each of six therapy sessions over a period of three weeks
▼ Outcome Measure Data	✓
► Analysis Population Description	
Arm/Group Title	IR REHAB Device
► Arm/Group Description:	Participants will receive 6 treatment...
Overall Number of Participants Analyzed	Participants will receive 6 treatment...
Mean (95% Confidence Interval)	16
Unit of Measure: Score on a scale	61.46 (47.70 to 72.63)
Arm/Group Title	Sham Device
► Arm/Group Description:	Participants will receive 6 treatment...
Overall Number of Participants Analyzed	Participants will receive 6 treatment...
Mean (95% Confidence Interval)	13
Unit of Measure: Score on a scale	19.79 (4.89 to 37.34)

[figure not shown]

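### The SAP endpoint needs a pain rating after session six and pain is rated only at sessions, so anyone who stops early has no endpoint and the primary analysis compares completers

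*Combined protocol and SAP*

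**What the plan says.** **Endpoint.** The protocol (Data Analysis and Data Monitoring) compares the groups on mean change in "pain levels as recorded at the trials beginning and then at the trials conclusion", without dating the conclusion. The SAP (Analysis) is more specific: the change runs from the initial rating, and "the level of pain indicated after their sixth and final treatment will be statistically analyzed".

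**Collection of VAS.** The protocol (Methods and Procedures - continued) asks for a VAS before and after each session. The SAP (Analysis) asks participants for "their pain levels before the first treatment and after each of the prescribed treatments". The Outcome Measures table gives the time frame as "Participants will indicate their pain level before and after each of six therapy sessions over a period of three weeks". No VAS is scheduled away from a session. The four-month window in the Adverse Effects Overview concerns adverse events, collected non-systematically, and not pain.

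**Schedule.** Methods and Procedures states: "All participants will undergo treatments 2 times weekly for 3 weeks". That makes six sessions.

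**Not stated.** There is no rule for a missing session-six VAS, no provision for rating pain after someone stops, and no definition of an all-randomised or completer analysis set.

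**What was reported.** Participant Flow shows 16 active and 15 sham started, and 16 and 13 completed. Both non-completions were withdrawals by the subject in the sham arm. The Baseline Characteristics and Outcome Measures tables contain 16 and 13. The power comment under Outcome Measures describes the 29 as randomised.

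**The concern.** Randomisation protects the comparison of everyone who was assigned. Here, entry to the primary analysis depends on reaching session six, which happens after assignment. In a sham-controlled trial with a self-rated outcome, stopping may be related to perceived benefit or to suspecting sham, so those who finish need not be comparable between arms.

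The plan makes this happen by construction. Because each rating belongs to a session, stopping treatment also ends outcome collection, and under the SAP's definition the person's endpoint cannot exist. The protocol's looser wording does not help: with no off-session VAS, there is no end-of-trial rating for it to use either. At stake is whether the reported difference describes the randomised groups or only those who took the full course, and how far the unmeasured participants could move it.

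**Working it through.** **1. The two endpoint rules side by side**

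| Participant | Protocol: trial's conclusion | SAP: after sixth treatment | VAS planned at that time? |
|---|---|---|---|
| Completes six sessions | rating at session six | rating at session six | yes |
| Stops before session six | undated | cannot exist | no |

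The wordings part only in the second row, and there neither has a planned rating behind it.

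**2. Who is lost**

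Participant Flow: active 0/16; sham 2/15 = 13.3%; overall 2/31 = 6.5%. Fisher's exact test on 0/16 versus 2/15 gives p = 0.23. The imbalance is therefore not evidence of a difference in withdrawal rates.

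**3. Reproducing the reported figures**

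- Difference: 61.46 − 19.79 = 41.67, as reported.
- SD implied by the reported Cohen's d of 1.44: 41.67/1.44 = 28.94.
- Cross-check from the reported interval (20.15 to 61.67): standard error (61.67 − 20.15)/(2 × 1.96) = 10.59; SD 10.59/√(1/16 + 1/13) = 28.4. The two agree closely.
- Post-trial power with 16 and 13, SD 28.94, two-sided 0.05, noncentral t: 96.0%, against 95.7% reported. The reported power is that of the completer set.

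**4. Restoring the two sham withdrawals (16 versus 15)**

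Let both have pain reduction x. SD is 28.94 in the 16 active and the 13 sham completers.

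- Sham mean: m = (13 × 19.79 + 2x)/15
- Sham SD: s = √{[12 × 28.94² + 13(19.79 − m)² + 2(x − m)²]/14}
- Pooled SD: s_p = √{[15 × 28.94² + 14s²]/29}
- 95% CI: (61.46 − m) ± t(0.975; 29) × s_p × √(1/16 + 1/15)

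| x | m | Difference | s | 95% CI | p |
|---|---|---|---|---|---|
| 0 (no change) | 17.15 | 44.3 | 27.68 | 23.5 to 65.1 | 0.0002 |
| 61.46 (active mean) | 25.35 | 36.1 | 30.54 | 14.3 to 58.0 | 0.002 |
| 100 (full scale) | 30.48 | 31.0 | 38.91 | 5.9 to 56.1 | 0.017 |

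The largest fall is 41.67 − 30.98 = 10.7 points. The lower limit goes from the reported 20.15 to 5.9.

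**5. Room in the schedule**

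The minimum gap between a participant's "scheduled treatments will be 48 hours". Six sessions have five gaps: 5 × 48 h = 240 h = 10 days, out of 21.

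**The case against.** The strongest reply is that the two sections do not really conflict. The protocol gives no date for the trial's conclusion, all ratings fall at the six sessions, and the SAP can be read as the specific form of the protocol's general phrase. That stands for completers. It does not supply a rating, or a rule, for someone who stops.

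Second, a reader might infer that missing a single session forfeits the endpoint, or that a replacement session would have to fall after the three weeks. The documents do not support either. They are silent on rescheduling, the minimum gap leaves room for it (step 5), and a participant who misses an early session is still rated at later ones. Reporting Groups says each participant in the two reported groups had six sessions, and no endpoint is recorded as lost to a missed session. A projection of such losses would need miss rates that the documents do not give.

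Third, a reader might infer that a final rating could have been had from the two who withdrew. Participant Flow gives neither the timing nor the reason for withdrawal. Whether they attended any session, or would have given another rating, is unknown.

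Fourth, the direction may favour the sponsor. If the two stopped because they felt no benefit, their changes would lie near 0 and the difference would rise to 44.3, so leaving them out was conservative. The 10.7-point fall needs both sham withdrawals to go from worst pain to none. This stands.

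Finally, preferring an all-randomised endpoint to a full-course endpoint is partly a choice of question. The plan may keep the full-course question, but it should then be labelled as such.

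**Conclusion.** The point holds for participants who stop early. The SAP endpoint requires a rating after session six, and nothing provides for a rating once sessions end. The lack of later follow-up is an absence of provision, not a stated prohibition. The primary result is accordingly a completer comparison of 29 of 31 and not a comparison of the randomised groups.

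The effect on this trial is modest. With the two sham withdrawals restored at reductions from 0 to 100, the difference runs from 44.3 down to 31.0, the lower confidence limit from 23.5 down to 5.9, and p stays below 0.05. A reader might infer that the reported superiority depends on the exclusions; none of these scenarios supports that.

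The bounds rest on a common SD of 28.9 derived from the reported d, on assumed outcomes for two people, and on a single scale. The last needs confirming, because Outcome Measures gives the difference in points and Study Results gives it in percent. They also take the arm of the withdrawals from Participant Flow. The Adverse Effects Overview uses denominators of 18 and 13, which also total 31, so that assignment should be confirmed.

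**What to change.** **Plan wording.** Put one endpoint rule in both the protocol's Data Analysis and Data Monitoring section and the SAP's Analysis section: initial VAS minus VAS at the end of the three-week course, timed from the first session, for every randomised participant whatever number of sessions was received. State a window wide enough to contain session six for those who complete. Keep the after-sixth-treatment contrast as a secondary analysis.

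**Data collection.** In Methods and Procedures - continued, add one paper VAS at that time for anyone who stops early, unless they refuse.

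**Completed trial.** Describe the primary result as a completer analysis of 29 of 31, and report the three bounds from the working beside it with their assumptions. Carry a last observation forward only if post-baseline ratings exist for the two withdrawals, and label it a sensitivity analysis.

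**Cost.** Two wording changes, one extra form for the few who stop, and one short table in the report. The estimate will include people with less than a full course, and a few final ratings will not directly follow a session. The secondary contrast keeps the full-course answer available.

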## **Requirements for Human Subject Protection Training**

The Primary Investigator and clinical associates conducting the trial will complete the Collaborative Institutional Training Initiative (CITI) course GCP for Clinical Trials with Investigational Drugs and Medical Devices (U.S. FDA Focus).

## **Recruitment**

The Trial recruitment period had a start date of July 22nd and ended on August 7th 2024. (A total of 17 days) All participant recruitment and interviews were conducted at the Abbycare Clinic in Woodstock, GA.

## **Reporting Groups**

The first was the **IR REHAB Group** which was a randomly selected group of sixteen (16) participants who received treatment per the prescribed trial protocol using a fully functional invisa-RED Technology IR REHAB device. Treatment protocol is as follows: Participants will undergo six (6) therapy sessions of 15 minutes each over a three week period. Power settings will be based on the participants Fitzpatrick Scale skin type. For skin types i and ii a power setting of 7 was used, for skin types iii and iv a power setting of 6, for skin types v and vi a power setting of 4 was employed. Each participant randomly assigned to the IR REHAB group underwent six therapy sessions over three weeks using a fully functional invisa-RED Technology IR REHAB device.

The second group was the **Sham Group** which was a control group of thirteen (13) randomly selected participants who received a placebo treatment per the prescribed trial protocol using a non functional IR REHAB device. (The sham device was disabled and delivered no Low-level Laser Light energy during therapy but appeared to be fully functioning and powered-up.) Treatment protocol was as follows: Participants underwent six (6) therapy sessions of 15 minutes each over a three week period. Power settings were input based on the participants Fitzpatrick Scale skin type as per usual. For skin types i and ii a power setting of 7 was input, for skin types iii and iv a power setting of 6, for skin types v and vi a power setting of 4 was utilized. Each participant randomly assigned to the "Sham Group" underwent six therapy sessions over three weeks using the sham (non functioning invisa-RED Technology IR REHAB) device.

